10.10. UNSCHEDULED DETERIORATION VISIT

Patients will be trained by the Investigator to recognise worsening of expectoration and related symptoms.

If the patient and/or the investigator believe that it is in the patient's best interest to receive a rescue mucolytic, the patient will be discontinued from the study and rescue mucolytic will be administered, with any additional treatment the investigator deems appropriate and an unscheduled Deterioration Visit should be conducted whenever possible.

An unscheduled Deterioration Visit should be conducted also in case of worsening of the underlying condition. In particular, in case of bronchospasm in asthmatic patients the treatment must be discontinued and adequate therapeutic measures taken.

In case of unscheduled Deterioration Visit the following procedures will be performed:

- record details of any AEs since previous visit
- conduct dip-stick urine pregnancy test for females of childbearing potential.
- assess of vital signs ([Section 11.1.3](#));
- conduct physical examination (including chest auscultation);
- conduct 12-lead ECG in the supine position after 5 minutes of rest ([Section 11.1.6](#));
- conduct assessment of expectoration difficulty, sputum viscosity, sputum color and cough by means of the 4-point ordinal scales provided

In case during the unscheduled deterioration visit the patient and/or the investigator deem appropriate the discontinuation from the trial, all evaluations requested at Visit 4 should be performed (Section 10.11).

10.11. PREMATURE DISCONTINUATION VISIT

In case of premature discontinuation for any other reasons than those listed in 10.10 all evaluations requested at Visit 4 should be performed, excluding study medication administration.

A premature discontinuation visit must also be conducted in case of unexpected pregnancy.

11. METHODOLOGY

11.1. METHODS OF ASSESSMENT

11.1.1. DEMOGRAPHY AND MEDICAL HISTORY

At Visit 1 (Screening) the subjects' demographic data will be documented, including age, ethnicity, gender, height, weight as well as smoking history and alcohol use.

Further, the reason for hospitalization and medical history will be documented.

Any relevant worsening in ongoing conditions during the trial (i.e. since Visit 1) is required to be recorded as AEs in the eCRF (see [Section 18](#)).

11.1.2. PHYSICAL EXAMINATION

At Visit 1, Visit 2, Visit 3 and Visit 4, and/or at the unscheduled deterioration Visit/premature discontinuation, a physical examination of general body systems will be performed according to current medical standards and site practice. The examination is to include a chest auscultation. Any relevant worsening regarding physical examination results of a subject since Visit 1 should be recorded as AE in the eCRF (see [Section 18](#)).

11.1.3. VITAL SIGNS

At Visit 1, Visit 2, Visit 3 and Visit 4 and/or at the unscheduled deterioration visit/premature discontinuation, vital signs will be recorded according to site practice. Vital signs include:

- heart rate,
- systolic and diastolic blood pressure, measured after at least 5 minutes in the supine position,
- respiratory rate,
- body temperature, measured under the arm pit.

Automatic or manual devices may be used, but the same device should be used for any given subject throughout the trial. The same arm should be used for all measurements.

Any relevant clinically significant worsening of vital signs of a subject since the previous visit should be recorded as AE in the eCRF (see [Section 18](#)).

11.1.4. LABORATORY EVALUATIONS

Routine laboratory evaluations will be performed at Screening Visit (Visit 1) and Visit 4 and in case of premature discontinuation.

The blood samples must be collected after the 12-lead ECG has been performed.

The haematology and clinical chemistry parameters detailed in Table 1 will be analysed by the local hospital laboratory.

Subjects with clinically relevant impaired renal function, as defined by serum creatinine levels ≥ 3.0 x upper limit of normal at Visit 1 will not be randomized.

Subjects with clinically relevant impaired liver function, as defined by serum ALT and/or AST ≥ 3.0 x upper limit of normal at Visit 1 will not be randomized.

A dipstick urine pregnancy test for women of childbearing potential will be performed at Randomization Visit (Visit 2) and at Visit 4 and/or at unscheduled deterioration visit/premature discontinuation visit.

Female subjects who become pregnant during the trial must be withdrawn from the trial without delay and undergo the premature discontinuation visit; these patients are to be followed up to determine the outcome of the pregnancy. The Investigator is required to inform the Sponsor of a subject's pregnancy and the estimated date of delivery. Reporting requirements are outlined in [Section 18.10](#).

Clinical laboratory tests will be reviewed for results of potential clinical significance before Visit 2 to confirm patient's eligibility and during the trial, as appropriate. Clinically significant laboratory abnormalities arising at Visit 4 (or at premature discontinuation visit) are considered AEs. Where possible, a diagnosis should be ascribed to the abnormal lab test.

Table 1 CLINICAL LABORATORY EVALUATIONS

Hematology: at Screening Visit (Visit 1) and Visit 4 or premature discontinuation visit			
Hematocrit	Hemoglobin	Platelet count	Red blood cell count
White blood cell count and differential (neutrophils, lymphocytes, monocytes, eosinophils and basophils)			
Clinical Chemistry: at Screening Visit (Visit 1) and visit 4 or premature discontinuation visit			
BUN or UREA	Chloride	AST	
Creatinine	Uric acid	ALT	
Sodium	Amylase	γGT	
Potassium	ALP	Bilirubin (direct and total)	
Calcium			
Pregnancy Test: at Screening Visit (Visit 1), Visit 4 or premature discontinuation visit			
Urine β-hCG (dipstick)			

11.1.5. EFFICACY EVALUATIONS

Sputum viscosity, expectoration difficulty, sputum color, cough

Sputum viscosity, expectoration difficulty, sputum color and cough are assessed by means of ordinal categorical 4-point scales with 0 = best and 3 = worst.

For each patient the assessment is to be carried out by the blinded rater on treatment days 1 (baseline), 3 and 7 in the morning before 9 am before administration of study drug. Should a patient discontinue prematurely from the trial (including discharge from the hospital before day 7) an assessment should be conducted on the day of discontinuation whenever possible (see unscheduled Deterioration Visit, Section 10.10).

Scoring criteria are as follows (adapted from [12])

	0	1	2	3
Sputum viscosity	Liquid (normal viscosity)	Fluid (mildly increased viscosity)	Viscous (moderately increased viscosity)	Sticky (severely increased viscosity)
Expectoration difficulty	No difficulty	Mild difficulty	Moderate difficulty	Marked difficulty
Sputum color	Mostly white	Mostly pale yellow	Mostly dark yellow	Very dark yellow /green
Cough	No cough	Sporadic and mild cough	Moderate cough	Severe Cough

Sputum Volume

At Randomization Visit (Visit 2), Visit 3 and Visit 4 the patients will be given a graduated container and instructed to use it to collect all sputum generated in the following 24 hours (i.e. same time of the following day). The day the container will be collected, and the 24-hour sputum volume measured in ml.

11.1.6. SAFETY EVALUATIONS

Adverse Events

AEs will be recorded by Investigator in the appropriate eCRF Section from Visit 1 (date of informed consent) to the follow-up phone all or visit occurring 2 weeks (± 3 days) after the last administration of the investigational medicinal product (IMP). At each contact (i.e. clinical visit or phone call), subjects will be asked in a non-leading manner if they experienced any AEs.

All AEs occurring from the day of the first IMP administration, i.e. Visit 2, until the end of the trial, i.e. follow-up phone call, will be considered as treatment emergent TEAEs.

For definitions and reporting of AEs and SAEs, see [Section 18](#).

12-lead electrocardiogram (ECG)

12-lead ECG recordings will be obtained at each study centre using site machines at the Screening Visit (Visit 1) to verify the eligibility of the subject, and at Visit 4 or unscheduled Deterioration visit.

ECG will be performed after obtaining vital signs. Prior to recording, the subject should be at rest for at least 5 mins.

ECG will be evaluated by the investigator/local medical staff and the recording will be reported in the eCRF as "normal", "abnormal clinically significant" or "abnormal not clinically significant".

Abnormalities of clinical significance recorded at Visit 1, Visit 4 or unscheduled deterioration visit/premature discontinuation visit which are not related to pre-exist medical condition before ICF signature will be reported as AEs. Repeat measurements will be performed if needed.

11.2. ADHERENCE WITH IMP DOSING REGIMEN

As the administration of the IMP will be carried out by the study staff in a hospital setting, it is anticipated that adherence with IMP dosing regimen will be high.

Nevertheless, the Investigator will assess adherence with IMP dosing regimen on an ongoing basis by determining the amount of IMP dispensed, used (i.e. returned open ampoules/vials) and the amount of IMP returned (i.e. returned, unopened ampoules/vials) at Visit 2 (first dose), Visit 3 and Visit 4 (end of treatment) or unscheduled Deterioration Visit/premature discontinuation visit.

The evaluation of compliance will be done using the following formula:

$$\% \text{ of administered drug} = 100 \times \frac{\text{Total number of administered doses}}{\text{Total number of scheduled doses}}$$

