This trial is designed as rater- and patient-blind. i.e. whereas the staff administering the study drugs will know what each patient is receiving, neither the staff evaluating the patient, nor the patients themselves will know. The trial cannot be fully blinded (double-blind) because the appearance of NAC ampoules and ambroxol vials is different and more importantly because the NAC formulation releases a harmless but immediately distinguishable sulfuric smell. Rater- and patient-blinded designs are accepted for pivotal registration trials by the US-FDA, EMA and Regulatory Authorities worldwide in situations where full blinding is impossible.

The selected doses of iv NAC and ambroxol are within the limits of relevant SmPCs (10,18); dose justification is provided in [Section 5](#) below.

The treatment duration of 1 week has been selected after consultation with Chinese experts, as only a small minority of patients receive iv mucolytics for more than 1 week.

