13.2. INVESTIGATIONAL MEDICINAL PRODUCT DISPENSING AND ADMINISTRATION

All IMPs will be dispensed twice daily as one in the morning and another is in the afternoon/evening for a week of treatment period at hospital investigational sites by study staff. All IMP will be administered at the hospital investigational sites by study staff otherwise not involved with the efficacy assessment and care of study patients. The study staff members administering the IMP will be aware of its identity but will not disclose it to patients or to other study staff members who are involved in efficacy assessment (patient and rater-blind design, see [Section 4](#)).

NAC (Active test treatment)

Two ampoules (NAC 600 mg) will be diluted in 10 ml NaCl 0.9% saline solution and administered by slow (at least 5 minutes) intravenous infusion twice a day, morning before 9 am and afternoon/evening approximately 12 ± 1 hours apart for 1 week (7 days). Total daily NAC dose: 1200 mg/day.

Ambroxol hydrochloride (active control treatment)

Two vials (ambroxol 30 mg) will be diluted in 10 ml NaCl 0.9% saline solution and administered by slow (at least 5 minutes) intravenous infusion twice a day, morning before 9 am and afternoon/evening approximately 12 ± 1 hours apart for 1 week (7 days). Total daily ambroxol dose: 60 mg.

Placebo

One vial of 10 ml NaCl 0.9% saline solution will be administered by slow (at least 5 minutes) intravenous infusion twice a day, morning before 9 am and afternoon/evening approximately 12 ± 1 hours apart for 1 week (7 days).

Study staff administering the IMP will be instructed to store the empty used and the unused ampoules/vials for IMP accountability.

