Physical examination	X	X		X			X		x	X
Previous/concomita- nt medications	X	X		X			X	X		X
12-lead ECG	X						X		x	X
Blood sample for haematology and clinical chemistry	X						X			X
Assessment of expectoration difficulty, sputum viscosity, sputum color and cough by means of the 4-point ordinal scales provided			X				X		X	X
24-h sputum collection (to be collected and measured the following day)		X		X			X			X
IMP dispensation		X	X	X	X	X	X			
Accountability of IMP		X	X	X	X	X	X		X	X
AE monitoring	X	X		X			X	X	x	X

Appendix 2
Summary of Product Characteristics – N-Acetyl cysteine (NAC)
Switzerland

Fluimucil 10%

Qualitative and quantitative composition

Active ingredient: Acetylcysteine.

Excipients: Sodium edetate, Aqua q.s. to solution.

Pharmaceutical form and quantity of active ingredient per unit

Injection solution for i.v., i.m., local application.

Ampoules: 300 mg acetylcysteine per 3 mL (100 mg/mL).

Therapeutic indications

In respiratory tract diseases that lead to the formation of viscous secretions, which can not be or can only be insufficiently expectorated

Pneumology: All forms of bronchitis, emphysema, atelectasis, bronchiectasis, cystic fibrosis.

ENT diseases: Laryngitis, sinusitis, pharyngitis and laryngectomised patients.

Surgery: Prophylaxis of bronchopulmonary complications with mucostasis.

Paediatrics: Bronchitis, cystic fibrosis.

Intoxications: Antidote for paracetamol intoxications.

Posology and method of administration

Inhalative application

Adults: inhale 1 ampoule 1-2 times a day.

Children of an age where they can actively participate: inhale $\frac{1}{2}$ ampoule 1-2 times a day.

Instillations

Adults

Intraauricular and intranasal: 2-3 drops 2-3 times a day;

Endotracheal: 10-20 drops up to 1 ampoule 1-2 times a day;

Rinsing of other body cavities: $\frac{1}{2}$ ampoule per rinse.

Children

Intraauricular and intranasal: 1-2 drops 1-2 times a day;

Endotracheal: 10 drops up to $\frac{1}{2}$ ampoule 1-2 times a day.

Intravenous use

As a mucolytic in intensive care

Adults: 2-3 ampoules 2-3 times a day.

Children (see «Special dosage instructions»): 1-1½ ampoules 2-3 times a day.

It is recommended to dilute the ampoules with a 0.9% NaCl solution or with a 5% glucose solution and administer the solution slowly as a short infusion (over approx. 5 min.).

Intramuscular use

Adults: 1 ampoule 1-2 times daily by deep i.m. injection.

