4.10.1 Extent of Exposure

Exposure will be summarized both in terms of the treatment duration (in days) and the total dose administered up to the end of the last administration of IMP, as recorded on the eCRF. The duration of treatment will be calculated from the first administration date to the last administration date at the end of the last administration of treatment arm (duration = the last administration date - the first administration date +1). The total dose of the treatment arm will be the summation of actual administration dose at every administration.

Investigator will assess adherence with IMP dosing regimen on an ongoing basis by determining the amount of IMP dispensed, used (i.e. returned open ampoules/vials) and the amount of IMP returned (i.e. returned, unopened ampoules/vials) at Visit 2 (first dose), Visit 3 and Visit 4 (end of treatment) or unscheduled Deterioration Visit/premature discontinuation visit.

The evaluation of compliance will be done using the following formula:

$$\% \text{ of administered drug} = 100 \times \frac{\text{Total number of administered doses}}{\text{Total number of scheduled doses}}$$

The compliance calculation will be based on visit basis. For example, if subject takes IMP only in the morning but withdraws in the afternoon without taking IMP as planned, then the total number of scheduled doses at this visit will count two doses in the denominator.

A subject would be considered as compliant if % of administered drug is at least 80%.

The following summaries will be provided:

- A summary of the duration and the actual total dose by treatment group
- A summary of number and percentage of subjects with treatment compliance by treatment group and visit.

The following listings will be provided:

- A by-subject listing of administration of IMP
- A by-subject listing of treatment compliance

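### Protocol 11.2 and SAP 4.10.1 have the Investigator count containers that show the arm, while the Investigator can also decide rescue and withdrawal, which the primary analysis scores as no improvement at best

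*Protocol*

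**What the plan says.** **The count.** Protocol 11.2 states that "the Investigator will assess adherence with IMP dosing regimen on an ongoing basis by determining the amount of IMP dispensed, used", and defines the amounts by what is handed back: "used (i.e. returned open ampoules/vials) and the amount of IMP returned". This happens at Visits 2, 3 and 4, and at a deterioration or premature discontinuation visit. SAP 4.10.1 repeats that the "Investigator will assess adherence with IMP dosing regimen on an ongoing basis". The flow chart in Protocol Appendix 1 has a row "Accountability of IMP" marked on every dosing day and at both unscheduled visits.

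**The containers.** Under Protocol 13.2 a NAC dose is made as follows: "Two ampoules (NAC 600 mg) will be diluted in 10 ml NaCl 0.9% saline solution". An ambroxol dose is two vials, diluted in the same way. For placebo, "One vial of 10 ml NaCl 0.9% saline solution will be administered". Protocol 4 gives as one reason against full blinding that "the appearance of NAC ampoules and ambroxol vials is different".

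**Who may know.** Protocol 13.2 has doses given "by study staff otherwise not involved with the efficacy assessment and care of study patients", and bars disclosure to patients and to staff who assess efficacy. Sections 13.3 and 15.1 restrict unblinding by the Investigator. The warning in 10.2 labels staff who give doses, care for patients and do routine assessments as unblinded, and requires the rater to be someone else.

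**Withdrawal and scoring.** Under Protocol 10.10 and 16, the patient, the investigator or both may decide on rescue, and rescue ends participation. Section 16 also lets the Investigator withdraw a patient at discretion. Under SAP 4.9.1.3 a missing Day 7 score is replaced by the worst of baseline and later scores, including the rating at discontinuation (MVTF).

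**The concern.** Blinding the rater protects the recorded score. It does not protect the decision that determines whether a Day 7 score exists. Under MVTF, withdrawal alone removes any improvement the patient had made. If the person deciding knows the arm, withdrawals could differ between NAC and placebo without any drug effect, and the difference would pass straight into the primary superiority test. More withdrawal on placebo would favour NAC, and more on NAC would cost power. Section 11.2 supplies that knowledge routinely, with no code break.

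**Working it through.** **1. What the count shows.** Dosing is twice daily for 7 days, so 14 doses.
- NAC: 14 × 2 = 28 ampoules.
- Ambroxol: 14 × 2 = 28 vials.
- Placebo: 14 × 1 = 14 vials.

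The totals are complete only after the Day 7 rating, but they are not needed. The type of container, or two against one per dose, already separates the arms at Visit 2. By the morning of Visit 3, four doses have left 8 containers on either active drug and 4 on placebo.

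**2. Is the Investigator meant to know?**

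| Text | Points to |
|---|---|
| Protocol 13.3: Investigator may unblind only for a life-threatening SAE | not knowing |
| Protocol 15.1: code not broken except for an SAE | not knowing |
| Protocol 16: non-emergency unblinding is a reason for withdrawal | not knowing |
| Protocol 13.2: dosing staff not involved in care | not knowing |
| Protocol 13.2: disclosure barred only to patients and efficacy assessors | silent on the Investigator |
| Protocol 4: blinding promised for evaluating staff and patients | silent on the Investigator |
| Protocol 10.2: care and routine-assessment staff labelled unblinded | knowing |

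The text does not settle the question.

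**3. Route to the endpoint.** Rescue or discretionary withdrawal before the Day 7 rating leaves that score missing. MVTF then takes the worst of baseline and later scores, so the change is 0 at best, even if the blinded rater recorded improvement at discontinuation.

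**4. The plan's own power figure.** Inputs from Protocol 20.3: difference 0.35, SD 0.79 and 0.77, correlation 0.31, 100 per arm, one-sided 0.0125 per endpoint. Using n′ = 100 × 3/π = 95.5 for the Mann-Whitney test, power = Φ(0.35 / (SD × √(2/n′)) − 2.241).
- Viscosity: Φ(3.061 − 2.241) = 79.4%.
- Expectoration: Φ(3.141 − 2.241) = 81.6%.
- At least one, with correlation 0.31: 93.6% (93.5% by simulation). The plan states about 93%.

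**5. Illustration of unequal withdrawal.** The planned drop-out is 10%, or 0.10 × 111 = 11.1 patients per arm. The split by arm is not in the documents and is assumed. The simulation used 111 per arm and the SDs and correlation above. Also assumed were a mean change of −0.8 in both arms, baseline 2 or 3 with equal chance, and scores rounded and limited to 0–3. The test was van Elteren blocked on baseline, with success if either p ≤ 0.0125. MVTF gave withdrawn patients a change of 0. LOCF gave them a rating with half the mean change (−0.4, assumed). There were 40,000 runs per null case. With no withdrawals the error was 2.35% and power 92.7%.

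Chance of declaring NAC superior with no drug effect (nominal 2.5%):

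| Placebo / NAC withdrawal | MVTF | LOCF |
|---|---|---|
| 10% / 10% | 2.3% | 2.4% |
| 11% / 9% | 3.4% | not run |
| 12% / 8% | 5.3% | 3.4% |
| 13% / 7% | 7.7% | 3.9% |
| 15% / 5% | 14.8% | 5.2% |
| 8% / 12% | 0.9% | not run |
| 7% / 13% | 0.6% | not run |

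- At 12/8 the expected counts are 13.3 and 8.9 patients, and the shift in mean change is (0.12 − 0.08) × 0.8 = 0.032 points.
- Varying the mean change from −0.5 to −1.1 at 12/8 gives 4.6% to 6.3%.
- Fixing the counts instead of the rates gives 1.6% at 11 v 11, 3.8% at 13 v 9 and 5.7% at 14 v 8.
- Power for a true 0.35 effect under MVTF is 82% at 10/10, 95% at 13/7 and 60% at 7/13.
- A separate simulation assumed 60/40 baseline scores of 2/3 and mean change −0.7 to −1.3. It gave 2.1–2.6% at 5/5 and 6.1–8.6% at 10% placebo against 5% NAC.

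**The case against.** The strongest reply is that the trial promises blinding only of raters and patients. Section 15.1 says the study is not double-blind and explains the IWRS route for emergency unblinding as documentation. Section 10.2 openly treats care staff as unblinded, and Amendment 1 narrowed the bar in 13.2 from all other study staff to efficacy assessors. This stands in part. A reader might infer that 11.2 defeats a clear rule that the Investigator stays blind, but the documents do not support that, because the text conflicts and 11.2 is only one route to the knowledge. The route into the endpoint is no smaller if the knowledge was intended.

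A reader might also infer, from 15.1 naming Investigator and rater together, that the Visit 3 count unblinds the Day 7 rater. It does not, because 10.2 requires the rater to be a different person from dosing, care and routine-assessment staff.

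Other points that stand:
- The 10% drop-out covers every reason, including patient request, AEs and early discharge. The share decided by the Investigator is unknown.
- The blinded patient can also ask for rescue.
- The Visit 4 count comes too late to affect the Day 7 rating. Those that matter are at Visits 2 and 3, and at a deterioration or discontinuation visit, where the order of count and decision is not stated.
- LOCF and EM analyses, and discontinuation reasons by arm, are already planned. LOCF reduces the effect in the table but does not remove it.

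Section 13.4 lets a pharmacist or nominee keep the inventory. That helps the fix, but 11.2 still gives the adherence count to the Investigator and names no delegate.

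**Conclusion.** The point holds as a design exposure that is cheap to close. The plan routinely shows the arm to a role that can decide rescue and withdrawal, and the primary rule turns an early withdrawal into no improvement at best. It would be wrong to conclude that the trial will be biased: the documents show neither that decisions will differ by arm nor a direction.

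The size is conditional. With no drug effect and a total within the planned 10%, 12% against 8% takes the one-sided error from 2.5% to about 5% under MVTF and about 3% under LOCF. The reverse split takes it to about 1%, and equal withdrawal leaves it at or below nominal. These figures rest on the assumed split, mean change, baseline mix and LOCF rating.

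**What to change.** - **Protocol 11.2 and SAP 4.10.1:** give the container count to the unblinded dosing staff or the pharmacist, and pass only the percentage of doses given to the Investigator. The compliance formula uses doses administered over doses scheduled, so the Investigator needs nothing more.
- **Protocol 10.2:** align the warning with 13.2, so that only dosing and accountability staff are labelled unblinded. State that rescue and withdrawal decisions are made without knowledge of allocation, except in an emergency.
- **Protocol 10.10 and 10.11:** record the blinded rating before the decision where possible.
- **SAP 4.9.2:** keep MVTF as primary, and read the planned LOCF analysis beside the discontinuation reasons by arm in SAP 4.3.1.

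**Cost:** no new visit, data item, analysis or patient. Dosing staff already know the arm and already store the used containers. The downside is that sites must keep dosing and accountability staff apart from those who decide on rescue. At sites that followed the 10.2 wording this could mean rearranging duties, but 13.2 already largely requires it.
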